Study intervention	The screening phase is intended for diagnosing and assessing the patient for possible inclusion in the study and for providing an adequate washout period. The following study will be conducted in two parts. Part I is an open-label study, multiple center and dose escalation evaluation in twelve patients. Six subjects each will be evaluated for safety and efficacy assessments at 1 or 2 capsules TID dose for 28 days, sequentially. Each of them

	will be assessed twice in the first week after administration of PDC-1421 Capsules and once a week in the following treatment. Part II is a randomized, double-blind, placebo-controlled, parallel-group study. 60 subjects will be randomly assigned on a 1:1:1 basis to one of the three arms (1 PDC-1421 Capsule plus 1 placebo TID, 2 PDC-1421 Capsules TID, 2 placebo TID) for 6 weeks and evaluated the safety and efficacy every two weeks during the treatment period.
Primary endpoint	
 Change in Montgomery-Åsberg Depression Rating Scale (MADRS) total score from baseline to week 6 compared to placebo.
Secondary endpoints	
 Change in MADRS total score from baseline to week 2 and 7. Change in Hamilton Rating Scale for Depression (HAM-D-17), Hamilton Rating Scale for Anxiety (HAM-A), Depression and Somatic Symptoms Scale (DSSS), Clinical Global Impression Scale (CGI) total score from baseline to week 2, 4, 6 and 7. Percentage of partial responders (defined as a participant with a 25-50% decrease from baseline in total score) and responders (defined as a participant with $\geq 50\%$ decrease from baseline in total score) in MADRS by week 2, 4, 6 and 7. Evaluate Safety Assessments and Columbia-Suicide Severity Rating Scale (C-SSRS) from screening stage to the last visit Difference in the mean changes of MADRS, HAM-D-17, HAM-A, DSSS, CGI and C-SSRS from the baseline to week 2, 4, 6 and 7 between the PDC-1421 Capsule and placebo groups.
Safety Evaluation	
 Change from baseline in physical examination, vital sign, electrocardiogram (ECG), hematology and blood chemistry Incidence of AE/SAE
Statistical method	Descriptive Statistics

LIST OF ABBREVIATIONS/DEFINITIONS

- AE
Adverse Events, whether or not considered related to the investigational drug, must be recorded in CRF.
- CGI
Clinical Global Impression Scale (see Attachment III)
- CHO
Chinese Hamster Ovary
- Clinical monitor

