3.3 Secondary Endpoint

Table 12 The secondary efficacy endpoints in part II

Number	Items
1	MADRS total score—change from baseline to Visit 3 and 6 (Week 2 and 7).
2	HAM-D-17, CGI, DSSS and HAM-A—change from baseline to Visit 3, 4, 5 and 6 (Week 2, 4, 6 and 7)
3	Percentage of partial responders and responders (defined as participants with a 25-50% decrease and a $\geq 50\%$ decrease from baseline in total score, respectively) in MADRS total score by Week 2, 4, 6 and 7.
4	Safety evaluation—measurements of physical examination, vital signs, laboratory data, ECG, Columbia-Suicide Severity Scale (C-SSRS) and adverse events reports from screening stage to the last visit.
5	Difference in the mean changes of MADRS, HAM-D-17, HAM-A, DSSS, CGI and C-SSRS from baseline to week 2, 4, 6 and 7 between PDC-1421 Capsule and placebo groups.

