**5.3.3 Statistical Evaluation**

Simple descriptive statistics with 95% confidence interval will be performed with data collected in this study wherever applicable. Treatment effects are evaluated based on 2-sided test with a 0.05 significant level. All data shall be tabulated and presented in the study report. The descriptive statistics will be provided. The safety and efficacy data will be analyzed using the non-parametric method.

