**CONFIDENTIAL**

Project No. BLI-1005-002

Statistical Analysis Plan for PDC-1421

“Final” Page 23 of 34

Protocol Version: 2.3

SAP Version: 20180626\_01

second batch are “HDP-045A-070119” for PDC-1421 and “HDP-045C-070119” for placebo. Subjects with baseline visit later than 2018/02/13, or those who were enrolled before 2018/02/13 and got drugs after 2018/03/15 will be classified into the subgroup of the second batch.

The responder and partial responder is defined by the net change in total score of MADRS (responders are defined as participants with a  $\geq 50\%$  decrease in total score from baseline; partial responders are defined as participants with at least 25% and no more than 50% decrease in total score from baseline). The percentage difference between treatment groups will be examined by Cochran-Mantel-Haenszel test.

The same definitions of partial responder will be used for HAM-D-17. The difference between the treatment will be compared with Cochran-Mantel-Haenszel test as well.

All statistical tests used will be two-tailed with  $\alpha = 0.05$ .

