## 7. DOCUMENTATION OF STATISTICAL METHODS

### 7.1 Documentation of Statistical Methods

Following SAS procedures will be applied for statistical methods mentioned in Chapter 6.

SAS procedure	Statistical Analysis Method	Comment
Freq	Frequency table	
	Cochran-Mantel-Haenszel Test	Test of association between variables by controlling for multiple centers
Sgplot	Graph	
NPAR1WAY	Kruskal-Wallis test	To test group difference of continuous variables
	Wilcoxon rank sum test	Post-hoc test
MULTTEST	Holm's Procedure	Significant level control for Multiplicity
MEANS	Descriptive Statistics	Means, SD, Min, Max, Med, IQR, P1, P3

\*Center effect will be incorporated in only when degree of freedom is sufficient.

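### The 25–50% partial-response band has no fixed direction with benefit when read alone; SAP 6.4.2 does not state the CMH table or statistic, and its literal text names no HAM-D-17 responder rate

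*SAP*

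**What the plan says.** The protocol synopsis lists as a secondary endpoint the "Percentage of partial responders (defined as a participant with a 25-50% decrease from baseline in total score) and responders", the latter meaning a fall of 50% or more on MADRS, by weeks 2, 4, 6 and 7. Protocol 3.3 (Table 12) and SAP 5.3.2 repeat this.

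SAP 6.4.2 gives the band explicit limits: "partial responders are defined as participants with at least 25% and no more than 50% decrease in total score from baseline". It then says: "The percentage difference between treatment groups will be examined by Cochran-Mantel-Haenszel test". SAP 7.1 describes the CMH test only as a "Test of association between variables by controlling for multiple centers", with a footnote that the centre effect enters only if the degrees of freedom allow. No section says whether the table has two levels or three, which CMH statistic is used, or whether the proportion with at least a 25% fall is reported.

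On HAM-D-17, SAP 6.4.2 states that "The same definitions of partial responder will be used for HAM-D-17", and that "The difference between the treatment will be compared with Cochran-Mantel-Haenszel test as well". Neither document defines a HAM-D-17 responder at 50% or more, and neither endpoint list (Protocol 3.3, SAP 5.3.2) includes a HAM-D-17 response rate. HAM-D-17 change from baseline is a separate secondary endpoint at weeks 2, 4, 6 and 7, compared by Kruskal-Wallis and Wilcoxon tests.

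**The concern.** A drug that works moves some patients from below 25% into the band and others out of it into full response. The net change depends on where the arms sit, not only on whether the drug works. If the band is compared on its own, an effective dose may show the same or a lower rate than placebo. A significant difference in either direction would not tell the reader which arm did better.

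The plan applies a two-sided 5% level ("Treatment effects are evaluated based on 2-sided test with a 0.05 significant level"), so such a result could be reported as a finding. The exposure is greatest for HAM-D-17, where the band is the only response category named on the literal text. The overlap at exactly 50%, which meets both MADRS definitions, is a separate defect; this one would remain after it was mended.

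**Working it through.** **Inputs from the documents.** Cut-points 25% and 50% (SAP 6.4.2); two-sided 0.05 (SAP 5.3.3); 60 patients in Part II allocated 1:1:1, so 60 / 3 = 20 per arm (SAP 5.2). The documents give no expected response rates, SD or power, so there is no planned figure to reproduce.

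**Assumptions.** Percent reduction from baseline is normal with mean m and SD s. The values of m and s below are assumed.

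**Formulas.**
- At least 25%: P25 = 1 − Φ((25 − m)/s)
- Responder: P50 = 1 − Φ((50 − m)/s)
- Band: P25 − P50 = Φ((50 − m)/s) − Φ((25 − m)/s)

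P25 and P50 both rise whenever m rises. The band is their difference. Its slope in m is [φ((25 − m)/s) − φ((50 − m)/s)]/s, which is positive while m is nearer 25 than 50 and negative after that. The band therefore peaks at m = (25 + 50)/2 = 37.5, whatever s is.

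**One row in full** (s = 25, placebo 15, drug 30):
- placebo band = Φ(1.4) − Φ(0.4) = 0.9192 − 0.6554 = 0.264
- drug band = Φ(0.8) − Φ(−0.2) = 0.7881 − 0.4207 = 0.367

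| SD | Mean, placebo → drug | Band 25–50% | 50% or more | 25% or more |
|---|---|---|---|---|
| 25 | 15 → 30 | 26.4% → 36.7% (rises) | 8.1% → 21.2% | 34.5% → 57.9% |
| 25 | 30 → 45 | 36.7% → 36.7% (flat) | 21.2% → 42.1% | 57.9% → 78.8% |
| 30 | 35 → 50 | 32.2% → 29.8% (falls slightly) | 30.9% → 50.0% | 63.1% → 79.8% |
| 30 | 40 → 60 | 32.2% → 24.8% (falls) | 36.9% → 63.1% | 69.1% → 87.8% |

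The drug is better in every row, and both cumulative rates say so. The band gives three different answers.

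**Can the band alone be significant against a working drug?** Band counts of 2/20 on drug and 9/20 on placebo give a Fisher exact p of 0.031. Such counts could arise only because drug patients moved up to full response.

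**Simulation** (20 per arm, means 35/50/50, SD 30, three-arm tests, not stratified by centre). Proportion of trials rejecting at 0.05:
- band tested alone: about 5%, its chance level
- responder (50% or more): about 22%
- ordered three-level outcome: about 27%

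**The case against.** Several points on the other side stand.

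- **Layout.** A reader might infer that the SAP tests the band in its own two-level table. It does not say so. Responder and partial responder are defined in one sentence, and a three-level table is possible. The mock-up tables that might settle it (SAP 11.3) are an attachment not included here. What can be shown is that the table and the statistic are unstated.
- **HAM-D-17 wording.** The plural in the HAM-D-17 sentence may be shorthand for both MADRS definitions. On its literal words it covers partial response only.
- **MADRS.** The rate at 50% or more is planned at every post-baseline visit and has a fixed direction. Apart from patients at exactly 50%, the rate at 25% or more is the sum of the two reported percentages. A lower band beside a higher responder rate can be read as patients moving up.
- **HAM-D-17 as support.** A reader might infer that HAM-D-17 can no longer back up the MADRS result. The documents do not support that, because its change from baseline is tested separately.
- **Choice of scenario.** Results depend on the assumed means. Below a mean of 37.5% the band rises with benefit, as the first table row shows.
- **Gain from the ordered test.** The fair comparator is the planned responder test, about 22%, so the gain is about 27 − 22 = 5 percentage points. Setting 27% against 5% would overstate it.

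None of this gives the band a fixed direction or supplies the missing specification.

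**Conclusion.** The point holds in limited form. The 25–50% percentage, read alone, cannot be taken as benefit or harm. That follows from the definition and needs no distributional assumption; the sizes shown rest on the normal model and the assumed means and SDs. For MADRS the planned responder rate partly resolves the ambiguity. For HAM-D-17, on the literal text, the only response comparison is of this band, while the mean-change comparison is untouched.

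A reader might go further and infer that the trial's efficacy conclusion is at risk. It is not. SAP 6.1 rests the primary conclusion on the primary endpoint in the ITT population, SAP 6.4.1 tests it as MADRS change at week 6, and no success criterion or stated dose-selection rule uses partial response. The matter should be corrected, but it concerns secondary analyses in a small proof-of-concept study.

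**What to change.** In SAP 6.4.2, for MADRS and HAM-D-17 alike:

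1. Define one ordered outcome: decrease below 25%; 25% to below 50%; 50% or more.
2. Compare arms with the CMH row-mean-scores test, and name the statistic and score type in SAP 7.1, keeping the existing rule on when centre is included.
3. Report the cumulative proportions with at least 25% and at least 50% decrease, by arm and visit.
4. State that both the responder and the partial-responder definitions apply to HAM-D-17.
5. Keep the 25–50% percentage as a descriptive column only, so the percentage the protocol asks for is still reported.

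The half-open middle level also removes the overlap at exactly 50%. The cost is SAP wording and a matching table shell: the same data and the same SAS procedure (FREQ), read from a different CMH statistic. The change should be made before treatment codes are opened.

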## 6.5 Analysis of Safety

### 6.5.1 *Adverse events (AEs)*

The coding system used will be the Medical Dictionary for Regulatory Activities (MedDRA).

Pre-treatment AE is the AE onset before the first dosing of study drug, while treatment-emergent AE is the one onset after the first dosing of study drug. Pre-treatment AE and treatment emergent AE will be analyzed separately.

Frequency table of subjects with pre-treatment AE (PTAE) and treatment emergent AE (TEAE) will be presented by part, center and treatment.

For TEAE, adverse event incidents will also be summarized descriptively by system organ class and preferred term using MedDRA. If more than one type of event occurred within a system organ class/ preferred term for the subject, the subject is counted only once for each system organ class/ preferred term.

For TEAE, incidence tables of severity, action taken, relationship to study drug, outcome and serious AE or not will be presented by part, center, preferred term and treatment.

The frequency distribution of severity, action taken, relationship to study drug, and outcome of all AE events will be presented by part, center, and treatment.

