5.2.1 Screening Phase (Visit 1)

The Screening phase will be done within 1-2 weeks period and intended for diagnosing and assessing the patient for possible inclusion in the study and for providing an adequate washout period. The items of physical, rating scales, laboratory examination and drug accountability at screening are outlined below:

- Informed consent
- Subject information, including date of birth, body height and weight
- Medical history, including any clinically significant psychiatric, neurological, gastrointestinal, renal, hepatic, cardiovascular, respiratory, metabolic, endocrine, hematological or other major disorders
- Drug screen, including alcohol, benzodiazepine, amphetamine/MDMA, opiates, cannabinoid, cocaine, phencyclidine, and barbiturate. If a positive result is determined to be caused by prescription of benzodiazepine instead of subject's drug abuse, a 10-day washout period of the prescribed benzodiazepine is required before being treated with investigational products.
- Pregnancy test
- Physical examination: skin, head, neck, eyes, ears, nose, throat, heart, lungs, abdomen (liver, spleen), neurological examination, lymph node and extremities.
- Vital sign: heart rate, blood pressure, body temperature
- ECG
- Hematology: RBC, WBC, platelets, hematocrit, hemoglobin, prothrombin time (PT), partial thromboplastin time (aPTT)
- Blood chemistry: AST, ALT, LDH, total bilirubin, BUN, serum creatinine, free thyroxine (FT4), TSH, sodium, calcium, potassium, HbA1c, LDL, HDL, triglyceride, cholesterol.
- DSM-IV-TR, HAM-D-17, CGI, MADRS, DSSS, HAM-A, C-SSRS and concomitant medication evaluation.

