7.2 Methods and Timing for Assessing, Recording, and Analyzing of Safety Parameters

The data obtained before study drug administration in Visit 2 are set as baseline. After the beginning of treatment, the collection of data of safety parameters are performed at planned treatment schedule as section 5.2. AE or SAE will be closely monitored during the study period. CRC shall record these data in CRF in detail. In part I and part II, data are recorded from screening stage to the last visit.

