7.3 Adverse Events (AEs)

Adverse event is any unfavorable and unintended symptom, syndrome, medical condition or experience that develops or worsens within the study period. In this Phase II trial, any clinically significant abnormal findings, including causing the subject to withdraw from the study, requiring treatment or causing apparent clinical manifestations, or judged relevant by the investigator, are considered to be AEs and will be monitored and recorded. AE may not be causal relationship with study medication or clinical study. Whether related to study medication or not, CRC shall record the information of AEs in CRF. The information of AEs contains characteristic, onset and duration, frequency, the Investigator's opinion of the relationship to the study drug (unrelated, unlikely, possibly, probably, definitely), outcome (recovered, recovered with residual effects, continuing,

death, lost to follow-up) and severity. Common Terminology Criteria for Adverse Events v4.03 (CTCAE Table.17) is a descriptive terminology and the grading (severity) scale is provided for each AE term.

Table 17. Common Terminology Criteria for Adverse Events

Grade	Description
Grade 1	Mild; asymptomatic or mild symptoms; clinical or diagnostic observations only; intervention not indicated.
Grade 2	Moderate; minimal, local or noninvasive intervention indicated; limiting age-appropriate instrumental activities of daily living (ADL)*.
Grade 3	Severe or medically significant but not immediately life-threatening; hospitalization or prolongation of hospitalization indicated; disabling; limiting self-care ADL†.
Grade 4	Life-threatening consequences; urgent intervention indicated.
Grade 5	Death related to AE.‡

*Instrumental ADL refer to preparing meals, shopping for groceries or clothes, using the telephone, managing money, etc.

†Self-care ADL refer to bathing, dressing and undressing, feeding self, using the toilet, taking medications, and not bedridden.

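### SAP 6.5.1 sorts adverse events by onset date alone, so one that starts before first dose and worsens afterwards can be left out of the treatment-emergent tables

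*SAP*

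**What the plan says.** Protocol 7.3 defines an AE broadly. The definition covers any unfavorable "medical condition or experience that develops or worsens within the study period", so worsening alone is enough.

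SAP 6.5.1 then divides AEs by timing. On one side, "Pre-treatment AE is the AE onset before the first dosing of study drug"; on the other, "treatment-emergent AE is the one onset after the first dosing of study drug". It adds that "Pre-treatment AE and treatment emergent AE will be analyzed separately".

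The two classes are reported differently:

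- Both classes share one output: "Frequency table of subjects with pre-treatment AE (PTAE) and treatment emergent AE (TEAE) will be presented by part, center and treatment".
- The summary by system organ class and preferred term is specified for TEAEs only. So are the incidence tables of severity, action taken, relationship, outcome and seriousness.
- A further distribution of severity, action taken, relationship and outcome covers every AE, by part, center and treatment.
- SAP 6.5.2 tabulates SAEs without restricting them to TEAEs.

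On recording, Protocol 7.3 states: "The information of AEs contains characteristic, onset and duration, frequency", followed by relationship, outcome and severity. Neither document says whether worsening opens a new AE record or which onset date it takes.

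**The concern.** The protocol treats worsening as an AE in its own right, but the SAP's timing rule looks only at when the event began. The two definitions do not match for an event already present at first dose that becomes worse on study drug.

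Such events can occur here. Protocol 7.2 says of safety data: "In part I and part II, data are recorded from screening stage to the last visit". Protocol 5.2.1 adds: "The Screening phase will be done within 1-2 weeks period". SAP 6.5.1 itself expects pre-treatment AEs. Protocol 5.3 allows hypnotics for severe insomnia from Visit 1 to the first week after Visit 2, so the plan foresees at least one symptom that spans first dose.

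The TEAE tables are where a reader compares each dose with placebo for kind, grade and relatedness of events. Safety is the secondary objective in Protocol section 2 and SAP 5.1.2. A non-serious event that moves up a grade on treatment belongs in that comparison.

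**Working it through.** The plan states no figure on this point, so the check is a comparison of definitions, case by case.

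**Inputs.** The AE definition and recorded fields (Protocol 7.3); the safety recording period (Protocol 7.2); the length of screening (Protocol 5.2.1); the timing rule and table list (SAP 6.5.1); the SAE table (SAP 6.5.2); group sizes (Protocol 3.1).

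**Step 1. Apply the SAP rule as written.**

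| Case | Class under SAP 6.5.1 | In the TEAE tables? |
|---|---|---|
| A. New event after first dose | TEAE | Yes |
| B. AE starts in screening, does not worsen after dosing | Pre-treatment | No, correctly |
| C. AE starts in screening, worsens after dosing, kept as one record | Pre-treatment | No |
| D. As C, but the worsening is entered as a second record with its own onset | TEAE | Yes |
| E. Medical-history condition that first worsens after dosing | TEAE if onset is the date of worsening; pre-treatment if onset is the start of the condition | Not settled |

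Case C is misclassified by the rule itself. Whether an event falls under C or D depends on how the site enters it, and nothing in either document requires D. Case E turns on an onset-date convention that is not given.

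**Step 2. See where a case C event still appears.** It is counted in the pre-treatment frequency table, for which no severity or relationship breakdown is specified. It is also in the all-AE distribution, which has no preferred term and does not separate pre-dose from post-dose events. It reaches the SAE table only if serious. None of these outputs shows that a named, non-serious event worsened on treatment.

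**Step 3. Weight of one patient.** Part II randomizes 60 patients 1:1:1, so 60 / 3 = 20 per arm and one patient is 1 / 20 = 5 percentage points of that arm's incidence. Part I has six patients per dose, so one is 1 / 6, about 17 percentage points.

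**Step 4. Number of patients.** For Part II this would be 60 × p × q, with p the share who have an AE ongoing at first dose and q the share of those who worsen and are kept as one record. The documents give neither, so no count follows.

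**The case against.** The strongest reply is that Protocol 7.3 makes the worsening itself the adverse event, so AE onset naturally means the date of worsening. On that reading a pre-existing condition that worsens after dosing is already a TEAE. This stands for case E as a reasonable reading, though not a stated one. It does not help case C, where an AE with a pre-dose onset already exists.

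Second, case C may be uncommon. Medical history is taken at Visits 1 and 2, so symptoms present before dosing may be entered as history. Protocol Table 16 also appears to mark AE evaluation only from Visit 3. Against that, Protocol 5.2.3 lists AE evaluation at Visit 2 and Protocol 7.2 records safety data from screening.

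Third, the events are not lost from the report. Besides the outputs in Step 2, laboratory values, vital signs, physical examination, ECG and C-SSRS are analyzed by change, transition or shift whatever the AE class. Protocol 8.3 and SAP 5.3.3.1 also promise, in general terms, a coded summary of all AEs. This stands, and it would be wrong to say that the rule hides worsening altogether. But a pooled coded summary would mix screening events with on-treatment ones, and SAP 6.5.1 specifies preferred-term tables for TEAEs only.

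Fourth, a reader might infer that patients stop antidepressants during screening and so carry many withdrawal symptoms into dosing. Exclusion criteria 2 and 3 do not support that. Treatment for MDD must be absent for 2 weeks before Visit 1 (4 weeks for fluoxetine), and psychoactive drugs for 2 weeks apart from an insomnia exception. The only specific washout placed in screening is 10 days for prescribed benzodiazepines.

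Last, a new SAP definition alone may not be workable, because Protocol 7.3 does not say that grade is captured over time within one record. This is correct, and the fix has to cover it.

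**Conclusion.** The point holds in a limited form. SAP 6.5.1 states an onset-only rule that, followed as written, puts an AE that worsens after first dose into the pre-treatment class when it began in screening and is kept as one record. For medical-history conditions that first worsen on treatment, the plan leaves the class undetermined, so sites could treat like cases differently.

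A reader might go further and conclude that every condition that worsens on study drug leaves the TEAE tables. The documents do not support that: the loss is certain only under the single-record condition, and worsening entered as a new event is already counted.

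The weight of one patient, 5 percentage points in Part II, is a within-arm figure. Any distortion of the comparison with placebo depends on imbalance between arms, which cannot be judged from the plan. The AE summaries are descriptive, and the efficacy analysis is untouched. The mismatch is worth correcting because the TEAE tables carry the safety comparison and the correction is small.

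**What to change.** In SAP 6.5.1, define a TEAE as an AE with onset on or after first dose, or one present before first dose that increases in severity grade afterwards. The words on or after also settle the boundary between the two classes.

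To make this workable, state in the SAP and the CRF instructions that post-dose worsening, of an earlier AE or of a medical-history condition, is recorded as a new AE entry. Its onset is the date of worsening, and it carries its own CTCAE grade.

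The cost is one sentence in the SAP, one recording rule and a small amount of extra data handling; events already held as a single record may need a site query. TEAE counts may rise slightly. Subject-level incidence would not be counted twice, because SAP 6.5.1 already counts a subject once per class and term. The event-level all-AE distribution would count the earlier entry and the worsening separately, which a table footnote can say.
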